2.5. Randomization, Stratification, and Blinding

2.5.1. Randomization and Stratification

The study will randomize approximately 195 subjects, with approximately 65 subjects per treatment group, in a 1:1:1 ratio to GB004 480 mg BID, GB004 480 mg QD, and Placebo.

Randomization will be performed utilizing permuted block randomization via an interactive response technology (IRT) system. Randomization will be stratified by systemic corticosteroid use at baseline (yes/no).

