2.6. Sample Size Determination

A total sample size of approximately 195 subjects (approximately 65 per treatment group, randomized 1:1:1, with stratification by systemic corticosteroid use at baseline [yes/no]) is estimated to provide approximately 80% power to detect a difference of 20.4% between each GB004 treatment group and placebo for the primary endpoint of proportion of subjects with clinical remission at PCP Week 12 based on a chi-squared test at an 0.050 two-sided level of significance. This assumes the proportion of subjects with clinical remission at PCP Week 12 is 10% in the placebo group and 30.4% in each GB004 treatment group and a dropout rate by PCP Week 12 of approximately 8%. Subjects with missing clinical remission status at PCP Week 12 will be considered as having not met the primary endpoint.

Using the same sample size assumptions as above for the primary endpoint of proportion of subjects with clinical remission at PCP Week 12 (ie, a difference of 20.4% between each GB004 treatment group and placebo, with a 10% proportion in the placebo group), there will be approximately 80% power for the secondary endpoint of the proportion of subjects with clinical remission at PCP Week 36 based on a chi-squared test at an 0.050 two-sided level of

significance. Subjects with missing clinical remission status at PCP Week 36 will be considered as having not met the endpoint.

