- If the original values have 2 or more decimal places: mean, median, 25th and 75th percentiles, SD, and SE will all be reported to 3 decimal places.

Original values include both reported raw data values and derived values. In the case of derived values, an appropriate determination for precision will be made based on the reported raw data values used for derivation. Minimum and maximum will always be reported to the same number of decimal places as the original values, up to a maximum of 3 decimal places. Percent change

from baseline will be reported to 1 more decimal place than change from baseline, up to a maximum of 3 decimal places.

Efficacy results will be summarized by various measures, including, but not limited to, absolute differences in proportions, odds ratios (ORs), least squares (LS) means, differences in LS means, SEs, p-values, and two-sided, 95% CIs. Absolute differences in proportions and corresponding CIs will be reported to 1 decimal place. ORs and their corresponding CIs will be reported to 3 decimal places. Least squares means and differences in LS means and their corresponding CIs and SEs will be reported per the rules above, with the CIs following the same rounding rules as the corresponding means. P-values will be reported to 4 decimal places, with values less than 0.0001 displayed as < 0.0001 and values greater than 0.9999 displayed as > 0.9999. All statistical hypothesis testing for efficacy endpoints will be at an 0.050 two-sided level of significance.

Summaries of subject disposition, major protocol deviations, demographic and other baseline characteristics, UC treatment history, and concomitant UC background medications at baseline will be presented by randomized treatment group and will also include an overall column combining all treatment groups. Summaries of medical history and prior medications will be presented by actual treatment group and will include an overall column combining all treatment groups. Summaries of concomitant medications, duration of study treatment, compliance, prescribed dose modifications, and time on study will be presented by actual treatment group and will also include a total GB004 column combining both GB004 treatment groups. Efficacy tables will be presented by randomized treatment group only. Safety tables will be presented by actual treatment group and, in general, will also include a total GB004 column combining both GB004 treatment groups.

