8.3. Analysis Methods

8.3.1. Primary Endpoint

8.3.1.1. Primary Analysis

The primary objective of the PCP will be evaluated by testing the superiority of each GB004 treatment group to the placebo treatment group with respect to the primary endpoint of the proportion of subjects with clinical remission at PCP Week 12 based on a Cochran-Mantel Haenszel (CMH) chi-squared test ([Mantel, 1959](#)) stratified by the randomization stratification factor of systemic corticosteroid use at baseline (yes/no) with a two-sided 0.050 level of significance for each comparison.

The Mantel-Fleiss criterion ([Mantel, 1980](#)) will be used to assess the validity of the chi-square approximation for the distribution of the CMH test statistic. In the case that the Mantel-Fleiss criterion is not at least 5, indicating lack of validity of the chi-square approximation due to stratum cell sizes that are too small, Pearson's chi-squared test will be used instead of the CMH chi-squared test in the primary analysis of the primary endpoint. In the rare case that expected cell frequencies are too small, Fisher's exact test will be used instead of Pearson's chi-squared test.

For the comparison of each GB004 treatment group versus placebo, the p-value from the CMH chi-squared test (or Pearson's chi-squared test and/or Fisher's exact test, as described above) will be reported. The number and proportion of subjects meeting the primary endpoint and corresponding 95% Wilson (Score) CIs ([Wilson, 1927](#)) will be summarized by treatment group.

The unstratified, absolute difference in proportion between each GB004 treatment group and placebo will be summarized, with the 95% CI for the unstratified, absolute difference based on the Newcombe continuity-corrected method ([Newcombe, 1998](#)). The estimated Mantel-Haenszel common odds ratio across strata and corresponding 95% CI will also be summarized.

The primary analysis of the primary endpoint will be based on application of ICE handling followed by NRI.

A bar graph of the proportion of subjects meeting the primary endpoint by treatment group will be presented.

Primary endpoint data will be presented in a by-subject data listing.

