8.3.1.2. Sensitivity Analyses

Sensitivity analyses of the primary endpoint will be conducted to evaluate the robustness of treatment effects observed in the primary analysis of the primary endpoint described in [Section 8.3.1.1](#) above.

[Table 4](#) below provides an overview of the primary and sensitivity analyses of the primary endpoint.

Table 4: Summary of Primary and Sensitivity Analyses of the Primary Endpoint

Analysis	Description
Primary Analysis: Analysis with both ICE Handling and NRI Applied	
 Analysis based on application of both ICE Handling and NRI. P-value based on CMH chi-squared test. Estimated treatment effect based on unstratified, absolute difference in proportion, with 95% CI based on the Newcombe continuity-corrected method.
Sensitivity Analysis #1: Analysis with NRI Applied without ICE Handling Applied	
 Analysis based on application of NRI without application of ICE Handling. P-value based on CMH chi-squared test. Estimated treatment effect based on unstratified, absolute difference in proportion, with 95% CI based on the Newcombe continuity-corrected method.
Sensitivity Analysis #2: Analysis with ICE Handling Applied without NRI Applied	
 Analysis based on application of ICE Handling without application of NRI. P-value based on CMH chi-squared test. Estimated treatment effect based on unstratified, absolute difference in proportion, with 95% CI based on the Newcombe continuity-corrected method.
Sensitivity Analysis #3: As-Observed Analysis without ICE Handling or NRI Applied	
 Analysis using observed data, without application of ICE Handling or NRI. P-value based on CMH chi-squared test. Estimated treatment effect based on unstratified, absolute difference in proportion, with 95% CI based on the Newcombe continuity-corrected method.
Sensitivity Analysis #4: Logistic Regression with ICE Handling and NRI Applied	
 Analysis based on application of Treatment Failure Rules and NRI. Estimated treatment effect and p-value based on OR from logistic regression analysis.

Abbreviations: CI, confidence interval; CMH, Cochran-Mantel Haenszel; ICE, intercurrent event; NRI, non-responder imputation; OR, odds ratio.

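### The named treatment-effect estimate and its 95% CI ignore the steroid strata used for randomisation and for the CMH test; no stratified risk difference is planned (minor)

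*SAP*

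**What the plan says.** - **Randomisation.** SAP 2.5.1: "Randomization will be stratified by systemic corticosteroid use at baseline (yes/no"). Protocol 6.3.2 agrees.
- **Test.** SAP 8.3.1.1 uses a CMH test over the randomised steroid strata. It falls back to Pearson's or Fisher's test only if the Mantel-Fleiss criterion is below 5 or cells are too small.
- **Effect size.** The same section: "The unstratified, absolute difference in proportion between each GB004 treatment group and placebo will be summarized", with a continuity-corrected Newcombe interval. Table 4 repeats this for the primary analysis and Sensitivity Analyses #1 to #3: "Estimated treatment effect based on unstratified, absolute difference in proportion".
- **Where the stratum does enter an effect measure.** The Mantel-Haenszel common odds ratio (8.3.1.1), the logistic odds ratio of Sensitivity Analysis #4 (8.3.1.2.4), and the by-steroid-use subgroup results for clinical remission and response (8.4).
- **Secondary endpoints.** SAP 8.3.2.1 applies the primary approach. SAP 8.2 restricts histologic remission and mucosal healing to subjects with both baseline neutrophil subscores above zero. That subset is not a randomisation stratum.
- **Protocol.** Section 9.4.1.1 gives the absolute difference and the Newcombe method without saying that the difference is unstratified.

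**The concern.** The p-value and the absolute difference reported beside it come from different analyses: one conditions on steroid stratum, the other does not. Two things can follow.

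First, where randomisation has balanced the strata, the pooled variance keeps a between-stratum component that the design removed. If steroid use predicts remission, the interval is then wider than it need be.

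Second, in a subset defined by baseline histology the strata are no longer balanced by design. A chance difference in steroid share between arms then passes into the unstratified difference, while the CMH test adjusts for it. SAP 8.2 gives protection against baseline imbalance as a reason for restricting these endpoints, so an estimate that leaves steroid imbalance in sits awkwardly with that aim.

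At stake are the precision of the absolute difference and its agreement with the test, not the validity of the test.

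**Working it through.** **Inputs from SAP 2.6 and 3.** "approximately 65 per treatment group, randomized 1:1:1"; remission "is 10% in the placebo group and 30.4% in each GB004 treatment group"; "a dropout rate by PCP Week 12 of approximately 8" per cent; two-sided 0.050. The documents give neither the steroid share nor how prognostic steroid use is. Assumed: share 30-50%, prognostic odds ratio (OR) 1 to 5 with users remitting less often, and 40-52 subjects per arm in the histology subset.

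**1. The plan's own figure.** The claim is that the size "is estimated to provide approximately 80% power to detect a difference of 20.4% between each GB004 treatment group and placebo". With n = 65 × 0.92 = 59.8 and mean rate 0.202:

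z = [0.204√59.8 − 1.96√(2 × 0.202 × 0.798)] / √(0.10 × 0.90 + 0.304 × 0.696) = (1.5775 − 1.1129) / 0.5492 = 0.846, so power is 80.1%. It reproduces.

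**2. Would the CMH test be used?** Expected remitters in two arms: 65 × (0.10 + 0.304) = 26.3, half in each arm under the null. The Mantel-Fleiss value is therefore about 13, above 5. At the design rates CMH stands, and the mismatch arises.

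**3. Standard error, full ITT, strata balanced.** Unstratified: SE² = [p₀(1−p₀) + p₁(1−p₁)]/65 = 0.3016/65, SE 6.81 points. Stratified: replace each term by Σ wₛ pₛ(1−pₛ), where wₛ is the stratum share.

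| OR | Steroid share | Placebo rates, non-users / users | GB004 rates, non-users / users | Sum | SE ratio, stratified / unstratified |
|---|---|---|---|---|---|
| 1 | any | 10 / 10% | 30.4 / 30.4% | 0.3016 | 1.00 |
| 2 | 50% | 13.0 / 7.0% | 37.6 / 23.2% | 0.2955 | 0.990 |
| 3 | 30% | 12.4 / 4.5% | 36.5 / 16.1% | 0.2917 | 0.983 |
| 3 | 50% | 14.6 / 5.4% | 41.6 / 19.2% | 0.2869 | 0.975 |
| 5 | 30% | 13.0 / 2.9% | 38.6 / 11.2% | 0.2834 | 0.97 |
| 5 | 50% | 16.3 / 3.7% | 46.2 / 14.6% | 0.2727 | 0.951 |

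Overstatement (1/ratio − 1): 0%, about 1%, about 2% (1.7-2.5%) and 3-5%.

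**4. Interval width and coverage, full ITT** (100,000 simulated trials per scenario). Mean width as planned is 28.7-28.8 points. Dropping only the continuity correction gives 26.6-26.7, so the correction accounts for about 2.1. At a 40% share, the Mantel-Haenszel interval with Sato variance is about 0.2 points narrower than uncorrected Newcombe when there is no stratum effect, and 0.4-0.9 narrower at OR 2-5. The part due to strata is therefore about 0.2-0.7 points. Coverage of the planned interval goes from 96.8% (OR 1) to 97.2-97.6% (OR 5).

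**5. Subsets.** The SD of the between-arm difference in steroid share is √[2s(1−s)/n]: 9.0 points at s = 0.3, n = 52, and 11.2 at s = 0.5, n = 40. A one-SD imbalance moves the unstratified difference by that amount times the gap in remission rate between strata: 0.9-1.1 points for a 10-point gap, 1.8-2.2 for a 20-point gap. The mean shift over repeated trials is zero. Simulated SDs, stratified against unstratified (points):

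- OR 5, s = 0.5, n = 52: 7.33 against 7.61, variance 7% lower.
- OR 3, s = 0.5, n = 52: 7.51 against 7.63, variance 3% lower.
- OR 2, s = 0.5, n = 52: 7.61 against 7.64, variance 1% lower.
- OR 1, s = 0.5, n = 52: 7.62 against 7.58, variance 1% higher.

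**6. Agreement with CMH at the 5% level.** In subsets of 50 per arm at a 40% share, OR 1-5, the interval and the test disagree in 8-12% of trials as planned, 2-7% without the continuity correction, and 1.3-1.7% with Mantel-Haenszel/Sato. In the full ITT population with a moderate stratum effect (OR about 2.5) the figures are 4.9-6.5%, 0.4-1.0% and 1.1-1.3%. Stratifying brings no improvement there; the disagreement comes mostly from the continuity correction.

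**The case against.** The strongest reply is that the choice is deliberate and harmless. The word unstratified is written out in 8.3.1.1 and four times in Table 4. A stratified effect measure, the Mantel-Haenszel odds ratio, sits in the same paragraph and matches the CMH test, and a stratum-adjusted logistic model follows. The primary objective is judged by the CMH test, which is unaffected. The interval errs on the safe side, and a crude difference between crude proportions is easy to read.

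Most of this stands. What remains is that neither odds ratio yields an absolute difference, which is the scale of the 20.4-point design assumption.

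The subset argument also has limits. Chance imbalance is ordinary sampling variation, which the unstratified interval covers: 95.2-95.5% without the correction at 40-52 per arm. At 50 per arm one subject is 2 points; with OR 2-5 and a 40% share the two estimates differ by more than that in 10-30% of trials.

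A reader might infer more than the documents support:

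- **That the primary estimate is biased.** With stratified permuted blocks it is not.
- **That the absolute difference drives a go/no-go decision.** Neither document says so.
- **That the interval is much too wide because of the strata.** That needs rates such as 2% against 15% on placebo and 8% against 42% on GB004, a prognostic odds ratio of about 8.5. Nothing in the documents suggests one that large.

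**Conclusion.** The point holds as a minor one. The estimate named in Table 4 does not follow the randomisation or the test it accompanies, and no stratified risk difference is planned anywhere.

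In the full ITT population the cost is a standard error overstated by 0-5% over the assumed range, and about 1-2% at prognostic odds ratios of 2-3. The point estimate is practically the same, and the larger conservatism comes from the continuity correction. In the histologic-remission and mucosal-healing subsets the gain is somewhat more useful: better agreement with the CMH test and, if steroid use is at least moderately prognostic, a few per cent less variance. It is a gain in precision and coherence, not removal of systematic bias.

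The direction follows from the design. The sizes rest on assumed steroid share, prognostic strength and subset size, which the documents do not give.

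**What to change.** In SAP 8.3.1.1 and the Table 4 rows for the primary analysis and Sensitivity Analyses #1 to #3, and so by reference in 8.3.2.1, name the Mantel-Haenszel-weighted risk difference over the randomised steroid strata, with a stratified 95% CI, as the estimate paired with the CMH p-value. A stratified Newcombe interval stays closest to protocol 9.4.1.1; the Sato variance is the alternative. Keep the unstratified difference as a descriptive line, and as the estimate when the Mantel-Fleiss fallback drops stratification. SAP 10 should record the change, since it now states that nothing departs from the protocol.

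Cost: a few lines of text and a software option. Downsides: about 1% more variance in the subsets if steroid use is not prognostic, and, if Sato is chosen, coverage slightly below nominal in most scenarios (about 94.4-95% in the full ITT population, 94.2-94.7% at 40-52 per arm). Whether to keep the continuity correction should be decided separately.

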8.3.1.2. Sensitivity Analyses

Sensitivity analyses of the primary endpoint will be conducted to evaluate the robustness of treatment effects observed in the primary analysis of the primary endpoint described in [Section 8.3.1.1](#) above.

[Table 4](#) below provides an overview of the primary and sensitivity analyses of the primary endpoint.

Table 4: Summary of Primary and Sensitivity Analyses of the Primary Endpoint

Analysis	Description
Primary Analysis: Analysis with both ICE Handling and NRI Applied	
 Analysis based on application of both ICE Handling and NRI. P-value based on CMH chi-squared test. Estimated treatment effect based on unstratified, absolute difference in proportion, with 95% CI based on the Newcombe continuity-corrected method.
Sensitivity Analysis #1: Analysis with NRI Applied without ICE Handling Applied	
 Analysis based on application of NRI without application of ICE Handling. P-value based on CMH chi-squared test. Estimated treatment effect based on unstratified, absolute difference in proportion, with 95% CI based on the Newcombe continuity-corrected method.
Sensitivity Analysis #2: Analysis with ICE Handling Applied without NRI Applied	
 Analysis based on application of ICE Handling without application of NRI. P-value based on CMH chi-squared test. Estimated treatment effect based on unstratified, absolute difference in proportion, with 95% CI based on the Newcombe continuity-corrected method.
Sensitivity Analysis #3: As-Observed Analysis without ICE Handling or NRI Applied	
 Analysis using observed data, without application of ICE Handling or NRI. P-value based on CMH chi-squared test. Estimated treatment effect based on unstratified, absolute difference in proportion, with 95% CI based on the Newcombe continuity-corrected method.
Sensitivity Analysis #4: Logistic Regression with ICE Handling and NRI Applied	
 Analysis based on application of Treatment Failure Rules and NRI. Estimated treatment effect and p-value based on OR from logistic regression analysis.

Abbreviations: CI, confidence interval; CMH, Cochran-Mantel Haenszel; ICE, intercurrent event; NRI, non-responder imputation; OR, odds ratio.

8.3.1.2.1. Sensitivity Analysis #1: NRI Applied without ICE Handling Applied

In this sensitivity analysis, the primary endpoint will be analyzed similarly as in the primary analysis but with application of NRI without ICE handling.

8.3.1.2.2. Sensitivity Analysis #2: ICE Handling without NRI Applied

In this sensitivity analysis, the primary endpoint will be analyzed similarly as in the primary analysis, but with ICE handling applied without NRI applied.

8.3.1.2.3. Sensitivity Analysis #3: As-Observed Analysis without ICE Handling or NRI Applied

In this sensitivity analysis, the primary endpoint will be analyzed similarly as in the primary analysis but based on observed data without application of ICE handling or NRI.

8.3.1.2.4. Sensitivity Analysis #4: Logistic Regression with ICE Handling and NRI Applied

In this sensitivity analysis, logistic regression modeling will be used to compare each GB004 treatment group with the placebo treatment group, after handling of ICEs and NRI are applied.

The logistic regression model will include covariates for treatment group, the randomization stratification factor of systemic corticosteroid use at baseline (yes/no), baseline Modified Mayo score, and region (Europe vs Rest of World).

The odds ratio (OR), corresponding asymptotic 95% CI, and p-value from the logistic regression model will be presented for the comparison of each GB004 treatment group versus placebo.

If the logistic regression model does not converge, covariates will be removed from the model, and the first reduced model that converges among reduced models with the below specified covariates will be utilized in the following order of priority:

- Treatment group, randomization stratification factor, and baseline Modified Mayo score
- Treatment group and randomization stratification factor
- Treatment group only

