8.3.2.2. Sensitivity Analyses

Sensitivity analyses of secondary efficacy endpoints will be conducted to evaluate the robustness of treatment effects observed in the primary analyses of secondary efficacy endpoints described in [Section 8.3.2.1](#) above. These sensitivity analyses will be performed using the same approaches as the sensitivity analyses of the primary endpoint, with the differences described below.

For Sensitivity Analysis #4 (Logistic Regression with ICE Handling and NRI Applied), covariates in the logistic regression models for secondary efficacy endpoints will be the same as for the primary endpoint with the following exceptions:

- histologic remission will utilize the covariate of baseline RHI score instead of baseline Modified Mayo score;

- endoscopic improvement will utilize the covariate of baseline endoscopic subscore instead of baseline Modified Mayo score;
- mucosal healing will utilize the covariates of baseline RHI score and baseline endoscopic subscore instead of baseline Modified Mayo score.

If any of the logistic regression models for sensitivity analyses of secondary efficacy endpoints do not converge, the approach utilized for selection of a reduced model that converges will be similar to that for the primary endpoint. For mucosal healing, baseline endoscopic subscore will be removed from the model prior to removal of baseline RHI score.

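### The fallback for the logistic sensitivity analysis (SAP 8.3.1.2.4, carried to 8.3.2.2) ends at a treatment-only model, which has no finite odds ratio for an arm with no responders

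*SAP*

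**What the plan says.** SAP 8.3.1.2.4 compares each GB004 arm with placebo by logistic regression, after intercurrent-event handling and non-responder imputation. The covariates are treatment group, the corticosteroid stratum, baseline Modified Mayo score and region. An odds ratio, an asymptotic 95% CI and a p-value are to be reported for each comparison.

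The section then adds: "If the logistic regression model does not converge, covariates will be removed from the model". The first converging model from an ordered list is used:

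1. treatment, stratum and baseline score (region dropped);
2. treatment and stratum (baseline score also dropped);
3. treatment only.

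Nothing follows step 3. Convergence is not defined and separation is not mentioned.

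For the secondary endpoints, SAP 8.3.2.2 says "the approach utilized for selection of a reduced model that converges will be similar to that for the primary endpoint". It changes the baseline covariate by endpoint and, for mucosal healing, removes the endoscopic subscore before the RHI score. SAP Table 1 lists one primary endpoint, four secondary endpoints at Week 12 and five at Week 36, so the rule covers ten endpoints.

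**The concern.** The usual reason for a logistic model to fail on a binary endpoint with few events is separation: some combination of covariates contains no responders, or only responders. Dropping covariates helps when a covariate is responsible. It cannot help when treatment is responsible, because treatment is in every model on the list.

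Two things are at stake. The plan may reach the end of its own rule with nothing to report. Worse, software that stops when the likelihood flattens may report convergence. It would then print a huge odds ratio with an enormous standard error, and a strong effect would look null in an analysis meant to test robustness.

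**Working it through.** **Inputs (SAP 2.6).** The arms are "approximately 65 per treatment group, randomized 1:1:1". The assumed remission rates are "10% in the placebo group and 30.4% in each GB004 treatment group". The plan allows for "a dropout rate by PCP Week 12 of approximately 8" percent. On missing data: "Subjects with missing clinical remission status at PCP Week 12 will be considered as having not met the primary endpoint". Subjects without a Week 12 status therefore stay in the model as non-responders.

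**The plan's own figure.** SAP 2.6 claims "approximately 80% power to detect a difference of 20.4" percentage points, "based on a chi-squared test at an 0.050 two-sided level of significance". The standard formula without continuity correction is

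n = [1.96·√(2·p̄·q̄) + 0.8416·√(p₁q₁ + p₂q₂)]² / d²

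With p₁ = 0.10, p₂ = 0.304, p̄ = 0.202 and d = 0.204:

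- n = (1.1129 + 0.4622)² / 0.0416 = 59.6, so 60 per arm (power 80.3%);
- allowing for 8% dropout, 60 / 0.92 = 65.2.

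This reproduces about 65 per arm, so the design rates can be used below.

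**Behaviour of the last step.** The treatment-only model was fitted by Newton-Raphson with 65 per arm. Eighteen responders is close to 65 × 0.304 × 0.92 = 18.2, and seven is close to 65 × 0.10 = 6.5.

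| Responders, placebo / GB004 / GB004 | Result |
|---|---|
| 7 / 18 / 18 | converges: log OR 1.155, SE 0.49, both arms |
| 1 / 18 / 18 | converges: log OR 3.199, SE 1.05, both arms |
| 0 / 18 / 18 | diverges: intercept −6.2, −16.2, −26.2 and SE of each log OR 1.7, 248, 36,837 at iterations 5, 15, 25 |
| 7 / 0 / 18 | empty arm diverges; the other arm stays at log OR 1.155, SE 0.49 |

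So one responder is enough for a finite estimate and none is not. Adding the stratum, baseline score or region cannot make the empty arm's coefficient finite, so all earlier steps fail as well.

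**If convergence is declared anyway.** For 0 / 18 / 18 the log-likelihood is stable to four decimals by iteration 15 (−76.7031). The Wald statistics for GB004 versus placebo are:

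- iteration 15: 15.243 / 248.2 = 0.06, p = 0.95;
- iteration 20: 20.243 / 3023.75 = 0.007, p = 0.99.

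For the same 0/65 versus 18/65, Fisher's exact test gives p = 0.000002, and the Newcombe continuity-corrected interval for the 27.7-point difference is 15.5 to 40.4 points.

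**Chance of an empty placebo arm, (1 − p)^n.**

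- Primary endpoint, design rate: 0.9^65 = 0.11%. With the rate diluted by 8% non-response, p = 0.10 × 0.92 = 0.092 and 0.908^65 = 0.19%. For a GB004 arm at 30.4% it is negligible.
- Rarer secondary endpoints: the documents give neither rates nor subset sizes, so every entry below is an assumption.

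| Assumed placebo rate | n = 50 | n = 40 |
|---|---|---|
| 10% | 0.5% | 1.5% |
| 5% | 7.7% | 12.9% |
| 3% | 21.8% | 29.6% |

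Smaller denominators are plausible. Under SAP 8.2, histologic remission and mucosal healing are evaluated only in subjects with both baseline neutrophil subscores above zero, and endpoints after Week 12 only in those who consented to protocol version 2.0.

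**What the replacement would give.** In the treatment-only model, Firth's penalty amounts to adding 0.5 to each cell. For 0/65 versus 18/65, OR = (18.5 / 47.5) / (0.5 / 65.5) = 51.0. The profile-likelihood 95% limits are 6.7 to about 6,560, and the penalised likelihood-ratio p is below 0.00001. The interval is very wide, but the result is defined and agrees in direction and strength with Fisher's test.

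**The case against.** The strongest reply is that no inference depends on this analysis. SAP 8.3.1.1 already handles sparse data where the hypothesis is tested: Mantel-Fleiss check, then Pearson, then Fisher, with Wilson and Newcombe intervals. SAP 8.3.2.1 extends that to the secondary endpoints. Sensitivity Analyses #1 to #3 do not use logistic regression. A pre-specified, ordered list is also a legitimate device, and the low-rate probabilities rest on assumed rates. Protocol 4.2.3 puts the placebo effect as high as 15% to 20% depending on the endpoint. At 15% the chance of an empty placebo arm is only 0.85^50 = 0.03% to 0.85^40 = 0.15%. All of this stands, and it limits the point to a minor one. It does not supply the missing last step. The Mantel-Haenszel odds ratio of 8.3.1.1 cannot stand in either: with no placebo responders its denominator is zero.

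A reader might go further in four ways that the documents do not support:

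- **That #4 is the plan's only covariate-adjusted analysis.** The CMH test is stratified (8.3.1.1), the continuous endpoints use ANCOVA with stratum and baseline value (8.3.4.1.2), and 8.4 allows optional logistic models with baseline Mayo score.
- **That the rule readily discards the stratum.** Region goes first and the stratum last.
- **That the rule is what makes odds ratios differ in meaning across endpoints.** SAP 8.3.2.2 already prescribes different covariates by endpoint.
- **That the final model fails whenever events are few.** It converges with a single responder in the placebo arm; the failure needs none.

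**Conclusion.** The gap is real but conditional and small. If an arm has no responders, no model on the list has a finite odds ratio for it. An empty placebo arm removes both comparisons. An empty GB004 arm removes only its own, although the SAP does not say that the other may still be reported from a model that has not converged.

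The probability is about 0.1% to 0.2% for the primary endpoint under the design rates. For rarer secondary endpoints it is about 0.5% to 30%, and that range rests entirely on assumed placebo rates of 3% to 10% and 40 to 50 subjects per arm. The fallback rule concerns Sensitivity Analysis #4 only. A reader might infer that the efficacy conclusions are at risk; they are not, because the primary tests and the risk-difference intervals remain valid when an arm is empty.

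**What to change.** State in SAP 8.3.1.2.4 and 8.3.2.2 that, when separation or non-convergence is flagged, Firth penalised-likelihood logistic regression with profile-likelihood confidence limits will be used with the full pre-specified covariates. At minimum, add it as the final step after the treatment-only model. Triggering on separation as well as on non-convergence matters, because it also catches a fit that the software wrongly reports as converged.

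The cost is a sentence in the SAP and one extra SAS option; no new data or subjects are needed. The downsides are wide intervals when an arm is empty, and some endpoints reported by penalised rather than ordinary likelihood. Those should be footnoted in the tables.
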